8 TREATMENT PLAN

8.1 Neoantigen DNA vaccine administration

The first neoantigen DNA vaccine injection will take place following completion of SOC therapy. The day of the first vaccine injection will be referred to as Day 1.

All subjects will be treated as outpatients in the Siteman Cancer Center.

The schedule of vaccination is Day 1, Day 29 \pm 7, Day 57 \pm 7, Day 85 \pm 7, Day 113 \pm 7, and Day 141 \pm 7 with at least 21 days between injection days. All study injections will be given intramuscularly using an integrated electroporation device (TDS-IM system, Ichor Medical Systems). At each vaccination time point, patients will receive two injections of the neoantigen DNA vaccine, one injection into each deltoid or lateralis. If both injections cannot be given on the same day, the patient will be asked to return to complete the second injection. Standard aseptic technique and precautions will be utilized in site preparation, vaccine administration, and medical waste disposal to ensure maximal safety of subjects and study personnel. Participants' vital signs will be monitored for 30 minutes post vaccine for safety purposes.

The propagation of electroporation inducing electrical fields in the muscle will result in brief, localized muscle contractions at the site of administration, which are transiently painful. The neoantigen DNA vaccines will be administered by an experienced nurse who has completed a training seminar on the use of the TDS-IM device.

The sites of immunization may be rotated for each of the immunizations. No injection will be given at a location in which the draining lymph nodes have been removed.

At the discretion of the treating physician, patients may be pre-medicated with lorazepam 1mg PO (or similar) at least 30 minutes but no greater than 60 minutes prior to the first injection. Patients may also receive a second dose of lorazepam (1 mg PO) (or similar) 10 minutes prior to injection. Patients may also receive pain medication at treating physicians' discretion PO at least 30 minutes but no greater than 60 minutes prior to the first injection.

At intervals throughout the study (both before and after vaccination) subjects will have blood drawn for immunologic assays. Any cells, serum or plasma not used will be stored for future immunological assays.

Please see **Section 10 Study Calendar** for details on study visit procedures and monitoring.

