10 STUDY CALENDAR

	Screening ^j	Eligibility Re-Check ^f	D1 ^h	D29	D57	D85	D113	D141	D169 ⁿ	EOT ^k	52 Weeks after completion of neoantigen DNA vaccine therapy	Long-term F/U ^e	
Randomization		X ^g											
Durvalumab ^{a,b}						X	X	X	X				
Vaccine ^d			X	X	X	X	X	X					
Concurrent meds	X		X	-----							X		
Physical exam, wt, PS	X	X	X	X	X	X	X	X	X	X			
Vital signs	X	X	X	X	X	X	X	X	X				
Medical History	X	X											
CBC w/diff, plts	X	X	X	X	X	X	X	X	X				
CMP ^c	X	X	X	X	X	X	X	X	X				
TSH, fT3, fT4	X	X				X ^{ab}	X ^{ab}	X ^{ab}	X ^{ab}				
Urinalysis	X	X				X ^{ab}	X ^{ab}	X ^{ab}	X ^{ab}				
ECG (in triplicate)	X	X				As clinically indicated ^a							
PT, aPTT, INR	X	X				As clinically indicated ^a							
Troponins I and T	X	X				Every 4 Weeks before treatment ^a							
AE evaluation ^o			X	-----							X		
Tumor measurements	X	As clinically indicated. Documentation (radiologic) must be provided for pts removed from study for PD.											
Radiologic evaluation	X	Radiologic measurements will be performed as clinically indicated.											
Conf. of persistent disease		X											
B-HCG	X	X	X	X	X	X	X	X					
Hepatitis serologies	X												
HIV testing	X												
Tissue collection	Research bx or surgical specimen or both												
Blood for sequencing	X												
Blood for immune monitoring ^p		X ^m	X	X	X	X	X		X		X		
a: Only if randomized to receive durvalumab													
b: To begin on Cycle 4, if neoantigen-specific T cell responses are detectable only if randomized to get Durvalumab													
c: Albumin, alkaline phosphatase, total bilirubin, bicarbonate, BUN, calcium, chloride, creatinine, glucose, potassium, total protein, SGOT [AST], SGPT [ALT], sodium													

d: +/- 7 days with at least 21 days between each injection
e: Annually for 5 years (\pm 2 weeks)
f: After completion of SOC therapy
g: After confirmation of eligibility and manufacture of vaccine
h: After completion of SOC therapy
j: May take place up to 28 days prior to registration.
k: Within 30 days of last day of study treatment
m: After the end of SOC chemotherapy
N: Durvalumab group only
O: In addition to completing an AE assessment at the vaccine dosing visit, an additional follow-up between 24-48 hours after vaccination must be performed (can be performed by phone). AE assessment and SAE reporting continues until 90 days after the last dose of Durvalumab or until time of initiation of other anticancer therapy, whichever occurs first.
p: \pm 28 days

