11.3.1 Tumor tissue and peripheral blood processing

Processing of tumor: The tumor will be sampled prior to initiation of therapy.

Tumor from the research biopsy will be prioritized for tumor exome and tumor cDNA-capture sequencing in order to identify tumor-specific mutant antigens and produce the neoantigen DNA vaccine. The cores will be placed in complete RPMI or equivalent media solution on ice and transported to [name] laboratory (CSRB, room 6664). Upon receipt by the lab, the tissue will then be prioritized for embedding in optimal cutting temperature (OCT) compound. The remaining cores will be placed into formalin for subsequent paraffin embedding (FFPE).

Cryomold will be filled slowly to the top with OCT compound. Tissue will be gently submerged into the OCT compound in the cryomold. OCT will then be hardened by placement on dry ice or in the vapor phase of liquid nitrogen. After hardening, the mold will be placed in a container and transferred to a -80°C freezer for storage. The frozen tissue will be transferred to the Laboratory of Translation Pathology (LTP, BJC-Institute of Health, Room 5110) or the CHiIPs Immunomonitoring Laboratory for storage.

In addition to tumor from a research biopsy, tumor from surgical specimens may be acquired.

Processing of peripheral blood: Blood samples will be collected at the following time points: baseline, following completion of standard of care therapy, and Days 1, 29, 57, 85, 113, 169 and at 52 weeks after completion of neoantigen DNA vaccine therapy. Seventy mL of peripheral blood will be collected in 7 green top heparinized tubes by venipuncture (BD Vacutainer® sodium heparin, REF 367874, approximately 10 mL each for a total of approximately 70 mL needed total) The research patient coordinator will transport the blood to the laboratory of [name] located in the Clinical Sciences

Research Building, Room 6664. PBMC will be obtained by Ficoll-Hypaque gradient centrifugation and cryopreserved in 10% DMSO in fetal bovine serum according to standard procedures. Plasma will also be collected and stored for the various immunologic testing to be performed.

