11.3.3 Neoantigen-specific T cell analysis

Peripheral blood will be processed and stored as PBMC and plasma. A frozen aliquot will be used for DNA isolation for both exome sequencing and HLA typing (the latter to be performed by ProImmune). The remainder of the samples will be used to analyze the immune response to neoantigen DNA vaccine alone vs. neoantigen DNA vaccine + durvalumab. We hypothesize that these two therapies will generate durable, neoantigen-specific CD4 and CD8 T cell responses, and affect the levels of immunomodulatory elements within the peripheral blood. We propose the following assays.

Multi-parametric flow cytometry will be used to measure an increase in polyclonal, activated T cells (CD3, CD4, CD8, HLA-DR, Ki67, PD-1, perforin, granzyme A/B), neoantigen-specific T cells (CD3, CD4, CD8,

MHC class I tetramers, MHC class II tetramers as described above) that persist over time (CD45RA, CD45RO, CCR7, CD27, CD28, CD95, CD58), and immunomodulatory elements (regulatory T cells: CD3, CD4, Foxp3, CD25; inflammatory monocytes, granulocytes: CD45, CD11b, CD115, CCR2, CD14, CD15) over various time points.

For functional analysis, Luminex and ELISPOT assays will be performed on PBMC using short peptides that mimic the minimal neoantigen epitope incorporated by the DNA vaccine with which the respective patient was vaccinated. The Luminex assay will be performed in conjunction with the Immune Monitoring Laboratory. ELISPOT assay will be performed as previously described [97-101] on PBMC from the subjects at all time points for IFN- γ . PBMC will be plated at various concentrations started at 300,000 cells per well, in triplicate, following the protocol previously described by [name] and colleagues for detection of breast cancer-specific T cells. PBMC will be co-cultured with the short peptides. As negative controls, PBMC will be incubated in medium alone or stimulated with matching wild-type peptides. As a positive control, we will include a mix of viral peptides (CEF) which contains immunodominant epitopes for multiple common MHC class I alleles from influenza virus, cytomegalovirus, and Epstein-Barr virus. After 24-48 hours, the plates will be developed and the spots counted in an ImmunoSpot Series I analyzer (Cellular Technology).

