15.2.1 Sample Size Calculations for Immunogenicity

A power analysis was performed using the paired t-test for over time differences (i.e., measures at Baseline vs. Day 1, Day 57) to test the first hypotheses that neoantigen DNA vaccines can induce and/or enhance neoantigen-specific T cell responses (e.g., the frequency of neoantigen-specific CD8 T cells in ELISPOT and multi-parameter flow cytometry). Assuming a moderate correlation between measures taken from the same individual, the designed sample size (n=24 patients) allows us 80% power at 1-sided 0.05 alpha level to detect a minimum of $0.5 \times SD$ for overtime changes. A power analysis was also performed using the 2-sample t-test for between-arm differences (i.e., measures at Day 113, Day 169) to test the second hypotheses that durvalumab will enhance the response to neoantigen DNA vaccines. We expect that the majority of the patients enrolled will remain in the study and lead to at least 10 evaluable patients/arm for such comparison. The designed sample size (n=10 patients/arm) provides us 80% power at 1-sided 0.05 alpha level to detect a minimum of $1.2 \times SD$ for between-group differences. Preliminary data from our phase 1 trial for mammaglobin-A DNA vaccine, though on patients with stable metastatic breast cancer and targeting a tissue-specific antigen, showed that the frequency of antigen-specific CD8 T cells can be measured with ~20% coefficient of variation ($CV=SD/Mean$). Therefore, the designed sample size allows us to detect ~10% for over-time differences and ~15% for between-group differences respectively. As a study to estimate preliminary information, we expect that ~20% difference will provide an adequate signal for immunogenicity. In addition, we anticipate that more power could be achieved because the actual data analysis will be performed using mixed model which uses data more efficiently and allows us to borrow information across multiple time points.

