15.3.2 Immune response

Neoantigen-specific T cell response to neoantigen DNA vaccines + durvalumab is the secondary objective of the trial. Neoantigen specific T cell responses will be measured by Luminex, ELISPOT, multiparametric flow cytometry, and CyTOF. The frequency of antigen-specific CD8 T cells in each arm at each time will be summarized using means, standard deviations and medians. The change over time as well as the difference between arms will also be compared using linear mixed model for repeated measurement data. The immunogenicity of the neoantigen DNA vaccine will also be analyzed qualitatively by summarizing the phenotypic and functional characteristics of epitope-specific CD8 T cells. Responses will be considered positive if the number of T cells after vaccination is greater than two standard deviations above the mean before vaccination [101]. The frequency of positive responses at each time point will be assessed and binomial response rates with 95% confidence interval estimates will be presented. In addition to presenting the binomial response rates, graphical and tabular summaries of the underlying distributions will be made.

To determine whether the observed difference is larger than might be expected by chance, a permutation test will be used to compare the observed test statistic to the distribution of test statistics that would be seen if there were no difference between the two arms. Specifically, we will randomly shuffle the data and calculate the test statistic from the shuffled data. This procedure will be repeated 10,000 times and the resultant testing statistics will provide an accurate representation of the null distribution. The observed test statistics of between-arm differences will be compared to the null distributions. For each outcome, the permuted p-value will be the fraction of permuted samples that resulted in a small statistic than the original sample [103].

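### The Study Calendar limits the Day-169 immune blood draw to the durvalumab group, but sections 11.3.1, 15.2.1 and 15.3.2 need it in both arms

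*Combined protocol and SAP*

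**What the plan says.** In section 10 (Study Calendar) the D169 column header carries footnote n, which reads "N: Durvalumab group only". The row for immune-monitoring blood has an X in that column. The row's only footnote is p, a window of 28 days either side. The D141 and end-of-treatment (EOT) columns have no immune draw.

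Other sections treat Day 169 as common to both arms:

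- Section 11.3.1 schedules blood at baseline, after standard of care, and on "Days 1, 29, 57, 85, 113, 169 and at 52 weeks after completion of neoantigen DNA vaccine therapy". It gives no arm limit.
- Section 11.3.3 plans ELISPOT on "PBMC from the subjects at all time points".
- Section 15.2.1 describes the two-sample t-test as "for between-arm differences (i.e., measures at Day 113, Day 169", and expects enrolment to "lead to at least 10 evaluable patients/arm for such comparison".
- Section 15.3.2 states: "The frequency of antigen-specific CD8 T cells in each arm at each time will be summarized using means, standard deviations and medians". It adds: "The frequency of positive responses at each time point will be assessed". A linear mixed model compares the arms over time.
- The Immune Monitoring Form in section 16 lists Day 169 with no arm limit. It omits Days 29 and 85, which 11.3.1 includes, so it is weaker support.

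Section 8.1 sends the reader to the calendar "for details on study visit procedures and monitoring". No passage says which text prevails when the calendar and another section differ.

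**The concern.** A footnote on a column header governs every row in that column unless a row is exempted. Read that way, the calendar tells staff not to draw Day-169 immune blood from vaccine-alone patients, although the analysis sections need that value. Blood that is not drawn cannot be recovered later.

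Two things are at stake. The second hypothesis, that durvalumab enhances the vaccine response, would lose its control value at one of the two time points on which it is powered. The vaccine-alone arm would also have no scheduled sample soon after the complete six-vaccination course.

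**Working it through.** **1. What footnote n adds.** In the D169 column the durvalumab, thyroid and urinalysis entries already carry footnotes a and b, and troponins carry a. All of these are therefore restricted to the durvalumab arm without n. Footnote n adds a restriction only for the remaining rows: examination, vital signs, CBC, CMP and immune blood. Of these, only immune blood conflicts with 11.3.1, 11.3.3, 15.2.1 and 15.3.2.

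**2. The plan's power figure.** Inputs from 15.2.1 are 10 per arm, one-sided alpha 0.05, 80% power and a detectable difference of 1.2 SD. For the two-sample t-test:

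- degrees of freedom = 10 + 10 − 2 = 18
- noncentrality = 1.2 / √(1/10 + 1/10) = 2.68
- power from the noncentral t = 82.5%
- difference detectable at 80% power = 1.16 SD, which rounds to the plan's 1.2
- 9 per arm gives 78.5%, so 10 is the smallest number per arm that reaches 80%

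The plan's sample size and rounded effect size are reproduced.

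**3. Numbers at Day 169 under the calendar.** With 24 patients randomised 1:1 (section 4.6), about 12 are vaccine-alone. Scheduled vaccine-alone samples at Day 169: 0, against at least 10 planned. The between-arm difference at Day 169 cannot be estimated, and the mixed model has no observed control value there.

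**4. What remains.** Day 113 is drawn in both arms and keeps 82.5% power at 1.2 SD. Using nominal days, and assuming blood is drawn before that day's dosing (the documents do not state this):

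| Draw | Vaccinations given before (Days 1, 29, 57, 85, 113, 141) | Durvalumab doses given before (Days 85, 113, 141, 169) |
|---|---|---|
| Day 113 | 4 of 6 | 1 |
| Day 169 | 6 of 6 | 3 |

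These are nominal counts. Footnote p lets the Day-113 draw fall anywhere from Day 85 to Day 141, and dosing has its own 7-day windows, so individual counts can differ.

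**5. The gap in vaccine-alone sampling.** The next scheduled draw is 52 weeks after vaccine therapy: 141 + 364 = Day 505. The gap is 505 − 113 = 392 days. With 7 days either side on the sixth vaccination and 28 days on both draws:

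- shortest: (134 + 364 − 28) − (113 + 28) = 470 − 141 = 329 days
- longest: (148 + 364 + 28) − (113 − 28) = 540 − 85 = 455 days

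**6. What a Day-169 control sample would add.** This needs a within-patient correlation ρ, which the documents do not give. Assume the same 1.2 SD effect at both days and average the two values, so that the SD is multiplied by √((1 + ρ)/2). Power is then 94.0%, 90.9%, 87.6% or 84.2% for ρ = 0.3, 0.5, 0.7 or 0.9, against 82.5% for Day 113 alone.

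**7. Secondary: adverse-event collection.** Footnote o and section 13 end collection 90 days after the last durvalumab dose, or at new anticancer therapy if earlier. For a patient given all four doses the 90-day limit is nominally 169 + 90 = Day 259. It has no date for vaccine-alone patients, or for durvalumab-arm patients without a T cell response who stay on vaccine (8.2, 8.3). The calendar's adverse-event row, as extracted, runs to the 52-week column, and nothing says how that fits with footnote o.

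**The case against.** The strongest reply is that this is a drafting slip and that staff would draw the blood anyway. Three places list or use Day 169 without an arm limit (11.3.1, 15.2.1 and the section 16 form). The only contrary text is a footnote on a visit that is also a durvalumab dosing day. That is a fair account of how the footnote may have arisen, and a reader should not infer a deliberate decision to leave controls unsampled, because no passage shows one. It does not remove the conflict: section 8.1 directs staff to the calendar and no precedence is stated.

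The second reply is that immune response is a secondary objective and Day 113 remains. This stands. A reader might infer that the between-arm test is lost, but section 15.2.1 names Day 113 too, and that comparison keeps its planned power at 1.2 SD.

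A reader might also argue that the Day-113 effect must be smaller because fewer durvalumab doses precede it. If a 1.2 SD effect at Day 169 were two thirds or one third as large at Day 113, power there would be 53.0% or 21.7%. Nothing in the documents says that the effect scales with the number of doses, so these figures are illustrations only.

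The third reply is that footnote p's window (Day 141 to 197) or the EOT visit covers the gap. It does not: the calendar schedules no immune draw for vaccine-alone patients at D141 or EOT, so there is no draw for the window to move.

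On adverse events, section 8.8 follows patients for 52 weeks, section 12.1 continues adverse-event follow-up after removal from therapy, and the new-therapy limit applies to everyone. These soften the secondary point to a wording conflict.

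**Conclusion.** The conflict is real and should be corrected before vaccine-alone patients reach Day 169. If the calendar is followed, that arm has 0 of about 12 Day-169 samples against at least 10 planned. The Day-169 contrast cannot be estimated, and the arm has no immune sample for nominally 392 days. The Day-113 contrast is intact at 82.5% power for 1.2 SD, but nominally after one durvalumab dose and four of six vaccinations.

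The size depends on staff following the calendar, on nominal visit days and on draws taken before dosing. The documents do not support a specific loss of overall power, because they give neither the time course of the effect nor the within-patient correlation.

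The adverse-event point is secondary. A reader might infer that the safety comparison is biased, but the safety analysis is descriptive (15.3.1) and the documents fix neither a direction nor a size for any effect.

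**What to change.** Keep footnote n for the durvalumab dosing visit, but exempt the immune-monitoring row. State that the Day-169 draw is taken in both arms, within footnote p's window and after the sixth vaccination. Removing n from the header altogether would do more than is needed, because examination, vital signs, CBC and CMP at D169 carry no other arm limit and would then apply to vaccine-alone patients too.

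The draw may be combined with the vaccine-alone EOT visit when that visit is held near Day 169. Footnote k sets EOT within 30 days of the last treatment, so its latest day is nominally 141 + 30 = Day 171 (Day 164 to 178 with the 7-day vaccination window), but it may be much earlier.

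The cost is amendment wording and one 70 mL draw, already listed in 11.3.1, for about 12 patients, plus an extra visit for any whose EOT is not near Day 169.

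Separately, reconcile footnote o, section 13 and the calendar's adverse-event row so that every patient, including those never given durvalumab, has a stated end of adverse-event collection.

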- Study Plan:** Twenty-four breast cancer patients will be enrolled. Tumor tissue and peripheral blood will be obtained prior to initiation of any treatment for sequencing and correlative studies. These analyses will inform the design of the neoantigen DNA vaccines.
- The neoantigen DNA vaccines will be manufactured at Siteman Cancer Center and then administered following standard of care therapy. It is anticipated that standard of care therapy in this clinical context will include surgery, adjuvant or neoadjuvant chemotherapy (AC + T or similar regimen), and adjuvant radiation therapy, taking a total of approximately 6 months to complete.
- Following standard of care adjuvant therapy, patients will be randomized to receive either a neoantigen DNA vaccine alone, or a neoantigen DNA vaccine + durvalumab. The vaccine will be administered by intramuscular injection on Day 1, Day 29 \pm 7, Day 57 \pm 7, Day 85 \pm 7, Day 113 \pm 7, and Day 141 \pm 7 with at

least 21 days between injection days. Each DNA vaccination will be 4 mg vaccine administered intramuscularly using a TriGrid electroporation device.

[figure not shown]
For patients who are randomized to neoantigen DNA vaccine + durvalumab, the neoantigen-specific T cell response will be assessed after two vaccinations (Day 57). If a neoantigen-specific T cell response is present, durvalumab will be administered every 28 days at a dose of 1500 mg beginning on Day 85.

Study Duration: Each subject will be followed for at least 12 months following the date of last treatment. Additional follow-up visits or telephone contact will be scheduled annually thereafter if the patient is alive and available for follow-up.

Study Endpoints: The phenotype and function of class I and II neoantigen-specific T cell response will be assessed by ELISPOT, luminex, multiparametric flow cytometry, and CyTOF. Safety endpoints include safety of the neoantigen DNA vaccine alone, or neoantigen DNA vaccine plus durvalumab. Toxicity will be graded according to the National Cancer Institute Common Terminology Criteria for Adverse Events version 4.03.

SCHEMA

Anti-PD-L1 antibody (MEDI4736)
Adjuvant personalized breast cancer vaccine (SLP with poly IC:LC)

PROTOCOL SIGNATURE PAGE

A RANDOMIZED PHASE 1 TRIAL OF NEOANTIGEN DNA VACCINE ALONE VS. NEOANTIGEN VACCINE PLUS DURVALUMAB IN TRIPLE NEGATIVE BREAST CANCER PATIENTS FOLLOWING STANDARD OF CARE THERAPY

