2.10.2 PK/Pharmacodynamic data

Based on available PK/pharmacodynamic data from ongoing Study 1108 with doses ranging from 0.1 to 10 mg/kg Q2W or 15 mg/kg Q3W, durvalumab exhibited non-linear (dose-dependent) PK consistent with target-mediated drug disposition. The PK approached linearity at ≥ 3 mg/kg Q2W, suggesting near complete target saturation (membrane-bound and sPD-L1), and further shows that the durvalumab dosing frequency can be adapted to a particular regimen given the linearity seen at doses higher than 3 mg/kg. The expected half-life with doses ≥ 3 mg/kg Q2W is approximately 21 days. A dose-dependent suppression in peripheral sPD-L1 was observed over the dose range studied, consistent with engagement of durvalumab with PD-L1. A low level of immunogenicity has been observed. No subjects have experienced immune-complex disease following exposure to durvalumab (For further information on immunogenicity, please see the current IB).

Data from Study D4190C00006 (Phase I trial in NSCLC subjects using the combination of durvalumab and tremelimumab) also show an approximately dose-proportional increase in PK exposure for durvalumab over the dose range of 3 to 20 mg/kg durvalumab Q4W or Q2W. (For further information on PK observations in Study 006, please see the current IB).

The observed durvalumab PK data from the combination study were well in line with the predicted monotherapy PK data (5th median and 95th percentiles) for a Q4W regimen.

A population PK model was developed using the data from Study 1108 (doses=0.1 to 10 mg/kg Q2W or 15 mg/kg Q3W (Fairman et al 2014)). Multiple simulations indicate that a similar overall exposure is expected following both 10 mg/kg Q2W and 20 mg/kg Q4W regimens, as represented by AUC_{ss} (4 weeks). Median C_{max,ss} is expected to be higher with 20 mg/kg Q4W (~1.5 fold) and median C_{trough,ss} is expected to be higher with 10 mg/kg Q2W (~1.25 fold). Clinical activity with the 20 mg/kg Q4W dosing regimen is anticipated to be consistent with 10 mg/kg Q2W with the proposed similar dose of 20 mg/kg Q4W expected to (a) achieve complete target saturation in majority of subjects; (b) account for anticipated variability in PK, pharmacodynamics, and clinical activity in diverse cancer populations;

(c) maintain sufficient PK exposure in case of ADA impact; and (d) achieve PK exposure that yielded maximal antitumor activity in animal models.

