13 REGULATORY AND REPORTING REQUIREMENTS

The entities providing oversight of safety and compliance with the protocol require reporting as outlined below. Please refer to 20.4 for definitions and 20.5 for a grid of reporting timelines.

Adverse events will be tracked from start of treatment through 90 days after the last dose of Durvalumab or until initiation of new anticancer therapy, whichever comes first. All adverse events must be recorded on the toxicity tracking case report form (CRF) with the exception of:

- Baseline adverse events, which shall be recorded on the medical history CRF

Refer to the data submission schedule in Section 16 for instructions on the collections of AEs in the EDC.

Reporting requirements for Washington University study team are found in section 13.1.

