13.1.4.2 Definition of adverse events of special interest

An adverse event of special interest (AESI) is one of scientific and medical interest specific to understanding of the Investigational Product and may require close monitoring and rapid communication by the investigator to the sponsor. An AESI may be serious or non-serious. The rapid reporting of AESIs allows ongoing surveillance of these events in order to characterize and understand them in association with the use of this investigational product.

AESIs for durvalumab include but are not limited to events with a potential inflammatory or immune-mediated mechanism and which may require more frequent monitoring and/or interventions such as steroids, immunosuppressants and/or hormone replacement therapy. These AESIs are being closely monitored in clinical studies with durvalumab monotherapy and combination therapy. An immune-mediated adverse event (imAE) is defined as an adverse event that is associated with drug exposure and is consistent with an immune-mediated mechanism of action and where there is no clear alternate etiology. Serologic, immunologic, and histologic (biopsy) data, as appropriate, should be used to support an imAE diagnosis. Appropriate efforts should be made to rule out neoplastic, infectious, metabolic, toxin, or other etiologic causes of the imAE.

If the Investigator has any questions in regards to an adverse event (AE) being an imAE, the Investigator should promptly contact the Clinical Study Lead.

AESIs observed with durvalumab include:

- Diarrhea / Colitis and intestinal perforation
- Pneumonitis / ILD
- ALT/AST increases / hepatitis / hepatotoxicity
- Neuropathy / neuromuscular toxicity (i.e. Guillain-Barré and myasthenia gravis)
- Endocrinopathy (i.e. events of hypophysitis, adrenal insufficiency, diabetes insipidus and hyper- and hypothyroidism and type I diabetes mellitus)
- Rash / Dermatitis

- Nephritis / blood creatinine increases
- Pancreatitis (or labs suggestive of pancreatitis - increased serum lipase, increased serum amylase)
- Myocarditis
- Myositis / Polymyositis
- Other inflammatory response that are rare / less frequent with a potential immune-mediated aetiology include, but are not limited to, pericarditis, sarcoidosis, uveitis and other events involving the eyes, skin, haematological and rheumatological events, vasculitis, non-infectious meningitis and non-infectious encephalitis.

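### The calendar does not support the 90-day safety window after a Day 141 or Day 169 last durvalumab dose: no contact is dated in its last 60 days, and no safety laboratory test follows a Day 169 infusion

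*Combined protocol and SAP*

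**What the plan says.** - **Length of the window.** Footnote O of the calendar says: "AE assessment and SAE reporting continues until 90 days after the last dose of Durvalumab". Section 13 says: "Adverse events will be tracked from start of treatment through 90 days after the last dose of Durvalumab", or until new anticancer therapy begins if that is earlier. Section 13.1.4 (SAE reporting to the durvalumab supplier) also closes at 90 days.
- **Last dose.** Section 8.7 allows up to four durvalumab doses. The calendar places them on Days 85, 113, 141 and 169.
- **Laboratory tests.** CBC, CMP, TSH/fT3/fT4 and urinalysis are last marked on Day 169. Troponins are drawn every four weeks before treatment. ECG and coagulation tests on treatment are done only if clinically indicated.
- **EOT visit.** Footnote k fixes only a latest date: "Within 30 days of last day of study treatment". The one assessment marked specifically in that column is physical exam, weight and performance status. The adverse event and concurrent-medication rows are continuous lines that cross it.
- **After EOT.** The next dated visit is 52 weeks after vaccine therapy is completed, followed by annual contact for five years. The only dated telephone contact is at 24 to 48 hours after a vaccination, and the last vaccination is on Day 141.
- **Events to be found.** Section 13.1.4.2 lists "ALT/AST increases / hepatitis / hepatotoxicity" among the events of special interest for durvalumab, along with creatinine increases and thyroid disorders.

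**The concern.** Safety is the primary objective, and Section 15.1.1 says that its assessment includes laboratory evaluation as well as clinical observation. A 90-day collection rule finds what patients report and what someone tests for. A site that followed the calendar exactly would do no test after the fourth infusion and have no dated reason to contact the patient in the last two thirds of the window.

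Some of the listed events can be present without symptoms. Section 13.1.4.5 makes this explicit for liver function: a potential Hy's Law case is reportable within 24 hours of knowledge even if the patient has no clinical signs. Without a test there is no knowledge, so the reporting duty is never triggered. At stake are the completeness of the safety data after the last infusion and the chance to notice such an event at the time.

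**Working it through.** **Inputs.** Dose days 85, 113, 141 and 169, visit days, and EOT at most 30 days after last treatment (Section 10). Window of 90 days (Sections 10, 13 and 13.1.4). Last vaccine on Day 141. Patients who stop injections early stay on the safety schedule (Section 8.7).

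**Formulas.** Window closes = last dose + 90. Latest EOT = last dose + 30. The 52-week visit = 141 + 364 = Day 505.

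| Last durvalumab dose | Window closes | Latest EOT | Calendar visits in the window (days after last dose) | Dated contact after day 30? |
|---|---|---|---|---|
| Day 85 | Day 175 | Day 115 | Day 113 (28), Day 141 (56), Day 169 (84) | Yes |
| Day 113 | Day 203 | Day 143 | Day 141 (28), Day 169 (56) | Yes |
| Day 141 | Day 231 | Day 171 | Day 169 (28) | No |
| Day 169 | Day 259 | Day 199 | None | No |

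**Full course (last dose on Day 169).**
- Undated stretch: 259 − 199 = 60 days, and 60/90 = 67%. It is longer if EOT is held early.
- Next dated visit: 505 − 259 = 246 days after the window closes, and 505 − 199 = 306 days after the latest EOT.
- Scheduled safety laboratory tests after the infusion: none. Apart from troponin, the calendar does not say whether the Day 169 draw comes before or after the infusion. A same-day draw could not show delayed toxicity from that dose in either case.

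**Last dose on Day 141.** The Day 169 panel falls on day 28, so one laboratory check follows the dose. The last 60 days of the window are again undated (231 − 171 = 60).

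**The plan's own safety figure.** Section 15.2.2 gives an 80% chance of at least one SAE among 10 patients at a true rate of 15%. This reproduces: 1 − (1 − 0.15)^10 = 0.803. It takes for granted that every event is recorded. The documents give no ascertainment share, so the shares *s* below are assumptions, with chance = 1 − (1 − 0.15*s*)^10:

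- *s* = 90%: 76.5%
- *s* = 80%: 72.1%
- *s* = 70%: 67.0%
- *s* = 50%: 54.1%

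This shows only how the stated figure depends on complete recording. It does not estimate the loss here, because many silent laboratory events would not be serious.

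**Background only.** Section 2.10.2 says: "The expected half-life with doses ≥ 3 mg/kg Q2W is approximately 21 days". Assuming simple exponential decay, 2^(−30/21) = 0.37 of the level remains at day 30 and 2^(−90/21) = 0.05 at day 90. Drug is still present when dated contact stops. This says nothing about how often toxicity occurs then.

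**The case against.** The strongest reply is that the 90-day rule is itself a duty to collect, whether or not every call is dated. The Toxicity Form is continuous (Section 16), the adverse event line crosses EOT, serious toxicities are monitored on an ongoing basis (Section 14.2), and toxicities are reviewed at a weekly phase 1 meeting (Section 14.3). This stands for symptomatic events, for events the patient volunteers and for admissions. A reader might infer that nothing is collected after EOT, or that late events will be missed. The documents support neither. What the reply does not cover is an asymptomatic laboratory change, which an open form cannot detect.

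Three other strong readings also fail:

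- **The combination arm is made to look safer.** The Day 169 visit is for the durvalumab group only, so the vaccine-alone arm has its last CBC and CMP on Day 141, the day of its own last dose. It too has no test after its final treatment, and it has no on-treatment thyroid, urinalysis or troponin testing. The safety analysis in Section 15.3.1 is descriptive. A direction of bias between arms is not shown.
- **Every durvalumab patient is affected.** Patients who stop after Day 85 or Day 113 and stay on the calendar have later visits inside their window.
- **The promised follow-up is cut short.** The synopsis says: "Each subject will be followed for at least 12 months following the date of last treatment". The 52-week visit comes 505 − 169 = 336 days, or 48 weeks, after a Day 169 dose, but annual contact continues for five years. The two passages use different starting points; follow-up is not lost.

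**Conclusion.** The point holds for durvalumab-arm patients whose last dose is on Day 141 or Day 169. For both, 60 of the 90 window days have no dated contact even when EOT is as late as allowed. After a Day 169 dose there is also no scheduled safety laboratory test. The consequence is that silent ALT/AST, creatinine or thyroid events can go unrecorded, which weakens ascertainment for the primary objective.

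The day counts assume nominal visit days. A late or early last infusion moves the window and the EOT limit together, so the 60 days do not change. The number of events that would be missed cannot be estimated, because the documents give no rate of immune events between 30 and 90 days after a last dose. This is a change that should be made; it does not undermine the design.

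**What to change.** Reconcile the calendar with the 90-day rule for patients who received durvalumab:

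1. Add one dated adverse event contact at 90 days after the last durvalumab dose. A telephone call is enough.
2. Mark the panel already used on treatment (CBC, CMP, TSH/fT3/fT4) at the existing EOT visit, and hold that visit toward the end of its 30-day limit.

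The cost is a calendar amendment, plus one blood draw and one call for each of about 12 patients (24 randomized 1:1). The downside is a few incidental laboratory findings.

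As a wording note only, reconcile the starting point of the 52-week visit (last vaccine) with that in the synopsis (last treatment).
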